# **PROTOCOL VERSIONS**

Version	Versions No	Version Date	Protocol updated &	Appendix No detail the
Stage			finalised by;	reason(s) for the protocol
				update
Current	1.0	09/12/2020	[name], D	Ethics submission
			[name]	
			UCL JRO	

# i. List of Abbreviations

ABPM	Ambulatory blood pressure monitoring
ВР	Blood pressure
CAVI	Cardio-ankle vascular index
cMRI	Cardiac magnetic resonance imaging
ECG	Electrocardiogram
НВРМ	Home blood pressure monitoring
LV	Left ventricle
LVMI	Left ventricular mass index
MRI	Magnetic resonance imaging
REC	Research ethics committee

# ii. Key Words

HeartGuide wrist Blood Pressure Monitor

Left ventricular mass

Cardiac MRI

Ambulatory Blood Pressure.

# iii. Trial Summary

Trial Title	Relationship between blood pressure profiles measured by a wrist-type blood pressure monitor (HeartGuide) and left ventricular mass index		
Internal ref. no. (or short title)	HeartGuide BP LVMI study		
Trial Design	Cross-sectional study		
Trial Participants	Men and Women ≥ 35 years old		
Planned Sample Size	50 study participants in the UK study. The data will be merged with a study conducted in parallel at the Jichi Medical University, Japan, using a similar protocol.		
Follow up duration	1 month		
Planned Trial Period	18 months; Anticipated start and end dates: 11 January 2021 – 10 July 2022 End of study defined as the last visit of the last participant		
	Objectives	Outcome Measures	
Primary	Association between mean "out of office*" systolic blood pressure measured by the HeartGuide watch BP monitor and left ventricular mass index (LVMI) measured by cardiac MRI. *out of office" refers to blood pressure measurements made by the study participants in their home and work environments, i.e. away from the doctor's office.	
 
LVMI by cardiac MRI
 
Mean of "out of office" systolic blood pressure measurements recorded by a wearable BP monitor (HeartGuide)
 
	
Secondary	
 
Comparison of the relationships between BP indices measured by; (i) the HeartGuide watch BP monitor, or (ii) ABPM, or (iii) seated office BP, with
 
	
 
LVMI and other cardiac / vascular indices by cardiac MRI
 
HeartGuide BP
 
	

# 

	
 
LVMI by cardiac MRI
 
2. Relationship between all BP indices and Cardiac Ankle Vascular index (CAVI).
 
3. Relationship between CAVI indices and cardiac MRI parameters including LVMI, cardiac volumes and vascular indices.
 
24-hour ABPM
 
CAVI
 
ECG voltage measures of LVMI
 
Brachial office BP
 
	
	
 
4. Relationships between all BP indices and ECG voltage criteria for left ventricular mass
 
5. The relationships and any
 
	
	significant differences between various BP indices	
Data collected and storage	Analysis of the data will be done at University College London. Only processed data will be sent to Omron Healthcare Co Ltd., [name].	
	Non-identifiable data will be collected on electronic tablet using an electronic case report form in REDCap. Data will be transferred to secure University College London computers and stored on a shared drive. No data will be stored on the electronic tablet.	
	Identifiable data will be stored within Data Safe Haven at University College London or within the site file in a secure cabinet at the research offices (UCL).	

\_\_\_\_\_

# Key Roles and Responsibilities

**SPONSOR:** The sponsor is responsible for ensuring before a study begins that arrangements are in place for the research team to access resources and support to deliver the research as proposed and allocate responsibilities for the management, monitoring and reporting of the research. The Sponsor also has to be satisfied there is agreement on appropriate arrangements to record, report and review significant developments as the research proceeds, and approve any modifications to the design.

**FUNDER:** The funder is the entity that will provide the funds (financial support) for the conduction of the study. Funders are expected to provide assistance to any enquiry, audit or investigation related to the funded work.

**CHIEF INVESTIGATOR (CI):** The person who takes overall responsibility for the design, conduct and reporting of a study. If the study involves researchers at more than once site, the CI takes on the primary responsibility whether or not he/she is an investigator at any particular site.

The CI role is to complete and to ensure that all relevant regulatory approvals are in place before the study begins. Ensure arrangements are in place for good study conduct, robust monitoring and reporting, including prompt reporting of incidents, this includes putting in place adequate training for study staff to conduct the study as per the protocol and relevant standards.

The Chief Investigator is responsible for submission of annual reports as required. The Chief Investigator will notify the RE of the end of the study, including the reasons for the premature termination. Within one year after the end of study, the Chief Investigator will submit a final report with the results, including any publications/abstracts to the REC.

# **Background and Purpose of the Study**

Blood pressure (BP) measurement is one of the commonest procedures conducted in routine medical care. Identifying an elevated BP is important because a persistently elevated BP is associated with increased lifetime risk of myocardial infarction, heart failure, stroke, dementia, vascular disease and chronic kidney disease. Indeed, global surveys have identified an elevated BP as the most important preventable cause of premature death. BP has traditionally been measured whilst seated and rested in the doctor's office using a cuff around the upper arm^1. More recently, devices have become available that have allowed BP to be measured "out of office", i.e. in the patients' more usual environment such as at home or at work. This is done, either with an automated 24-hour BP monitor (ambulatory BP monitoring or ABPM), programmed to measure BP multiple times over a 24-hour period using an upper arm cuff, whilst the patient is ambulant and when sleeping, or by patient self-measurement of BP using an upper arm cuff, multiple times whilst at home (whilst seated in the morning or the

evening for a minimum of 3 days), so called home BP monitoring (HBPM). With these out of office measurements (ABPM or HBPM), the multiple readings are averaged to provide a mean BP reading. Recent guidelines on the clinical management of hypertension in the UK (NICE), Europe and the USA have all recommended that out of office BP measurement (either by ABPM or HBPM) should be undertaken to confirm the diagnosis of hypertension because (i) they can identify patients whose BP is only elevated in the doctors' office but not out of office, so called white coat hypertension, avoiding unnecessary treatment of patients with white coat hypertension; (ii) when compared with seated office BP measurement, ABPM and HBPM readings are better correlated with pressure-mediated organ damage; and (iii) when compared with seated office BP measurement, and HBPM readings are better correlated with providing the most compelling data.

Recently a wristwatch style monitor was developed for the measurement of out of office BP (HeartGuide, Omron, Japan). This is smaller, lighter and less intrusive than conventional ABPM monitors and does not depend on an upper arm cuff. Instead, the cuff is incorporated in the strap of the watch (see fig. 2) which allows the patient to activate self-measurement of their BP multiple times during the day, either whilst seated (e.g. similar to HBPM) or when ambulant (similar to ABPM). The device prompts the user via a short vibration at the wrist, to position their wrist at heart level, immediately prior to BP measurement. In a recent study, we showed that BP measured with this device correlated very well with BP measurements using upper-arm cuff-based ABPM when BP was recorded by the HeartGuide watch immediately after each activation of ABPM BP measurement. The present study will extend these findings and evaluate whether average systolic BP measured using the HeartGuide watch is correlated with left ventricular mass index (LVMI) and a comparison of the strength of that correlation with that observed for 24-hour ABPM mean systolic BP and seated office clinic systolic BP. LVMI is the main outcome measure because hypertrophy of the left ventricle is a validated biomarker of elevated pressure and is itself potently correlated with increased risk of adverse cardiovascular outcomes and mortality. The study will use cardiac MRI (cMRI) to measure LVMI because cMRI is recognised as the most accurate and reproducible means of measuring LVMI.

In addition to the measurement of LVMI as the primary outcome, this study will also examine the relationship between different BP parameters and vascular biomarkers of hypertensive injury using the non-invasive measurement of the Cardio-Ankle Vascular Index (CAVI).

The findings of this study will provide evidence of the validity of HeartGuide watch BP measurements when compared with conventional upper arm cuff-based BP measurements and for the first time evaluate the relationship between these various BP measurement techniques and markers of hypertension-mediated organ damage, specifically LVMI. These findings will be important to help define whether the HeartGuide watch BP monitor can provide an alternative means to characterise BP levels for the diagnosis of hypertension and monitoring the response of patients to antihypertensive therapy.

An interesting aspect of the study is that the measurement of BP with the HeartGuide watch BP monitor will be used to measure BP whilst rested and seated in the morning and evening, thereby mimicking the usual pattern of BP measurement recommended in guidelines for HBPM with a conventional upper-arm cuff-based device. However, the HeartGuide watch BP monitor also allows for BP measurements to be taken at other multiple times during the day. This is similar to the profile of BP measurements taken by ABPM but, with measurements over multiple days unlike ABPM which typically only measures BP over a single day. In this regard, the HeartGuide watch BP monitor will provide a different profile of BP measurement when compared to conventional HBPM or ABPM. It is a key additional objective of this study to define whether this new profile of BP measurement reveals any difference in the strength of the correlation between BP and LVMI.

This protocol describes the UK based study. A similar protocol will be used for a parallel study of similar size and design, developed with our collaborators at the Jichi Medical University in Japan. The plan is to evaluate the data from both studies independently but also combine the results of both studies to evaluate the relationship between BP measurement methods and indices and LVMI in different population cohorts representing Europe and Asia.

#### **Objectives and outcome measures**

#### **Primary Outcome Measure**

The association between mean "out of office" systolic BP measured by the HeartGuide watch BP monitor and LVMI measured by cMRI. "Out of office" refers to BP measurements made by the study participants in their home and work environments, i.e. away from the doctor's office.

#### **Secondary Outcome Measures**

- 1. Comparison of the relationships between mean BP indices measured by; (i) the HeartGuide watch BP monitor, or (ii) ABPM, or (iii) seated office BP, with LVMI by cMRI
- 2. The relationship between all BP indices as measured by all devices and the Cardio-Ankle Vascular Index (CAVI).
- 3. The relationships between CAVI indices and LVMI and corresponding cardiac and vascular indices by cMRI.
- 4. The relationships between all BP indices and ECG voltage criteria for left ventricular mass
- 5. The relationships and any significant differences between various BP indices

# **Study Design**

This is a single centre cross-sectional study in 50 people with elevated systolic BP i.e.  $\geq$  130 mmHg, or receiving antihypertensive therapy. The study evaluates the relationships between BP measured with different validated and CE-marked devices, used for their intended purpose, and LVMI, measured by cMRI. The study does not involve any treatments or interventions.

A parallel study of similar design and purpose is also planned to be undertaken Jichi Medical University, Tochigi, Japan. This will allow for comparison of BP relationships with LVMI across two different population cohorts. To facilitate this two-centre analysis, non-identifiable data from both studies will be merged.

# **Trial setting**

UCL Bloomsbury Phenotyping Centre, [name]. This is a purpose designed clinical research facility, incorporating the Chenies Mews Imaging Centre where MRI studies will also be performed.

# **Participant Selection**

Study participants will have an elevated seated office systolic BP (≥130mmHg), or be receiving antihypertensive therapy for previously diagnosed hypertension and should meet the following criteria:

#### **Participant Inclusion Criteria:**

- Men or women aged ≥ 35 years or older
- Wrist circumference 16-19 cm (i.e. suitable for HeartGuide watch BP monitor)
- Seated Office systolic BP (Omron HEM-907) ≥ 130 mmHg or previously diagnosed with hypertension and currently taking anti-hypertensive medication.
- Willing and able to provide informed consent

#### **Participant Exclusion Criteria:**

- Unable or unwilling to provide informed consent
- Women who are pregnant
- Wrist circumference > 19 cm (unsuitable for the HeartGuide wrist monitor)
- Upper arm circumference > 42.0 cm (Unreliable cuff-based BP measurement)
- Unwilling or unable to undergo a cardiac MRI scan
- Current atrial fibrillation or other significant arrhythmia (makes BP measurement unreliable)
- Unwilling or unable to undertake 24-hour ambulatory blood pressure monitoring
- Unwilling or unable to undertake a minimum of 3 week-days of wrist blood pressure monitoring (HeartGuide watch BP monitor)
- Currently enrolled in another clinical trial or study

# **Study Processes**

Each participant will be required to attend three outpatient visits for this study. The study visits can be performed on multiple days at the patient's convenience and according to their availability. Figure 1 summarises the design of the study and table 1 summarises the study visits and procedures. All study visits and procedures should ideally be performed within one month of visit 1.

#### **Consent Procedure:**

At least 24-hours prior to obtaining written informed consent, potential study participants identified at University College London Hospital (UCLH), will receive the study patient information leaflet. UCLH will act as a recruitment PIC site for this study. Immediately prior to obtaining written informed consent, the study objectives and procedures will be discussed with potential study participant by a member of the study team. If the study participant agrees to proceed with the study, the consent form will be signed by the study participant and co-signed by a GCP-trained and designated member of the study team. The study participant may withdraw consent at any time during the study.

#### **Study visits**

#### Visit 1:

- The study inclusion and exclusion criteria will be reviewed and the study objectives will be discussed prior to signing of informed consent
- Details of participant demographics and medical history will be recorded in the electronic study case report form. This will include; details of prior hypertension and other cardiovascular risk factors, i.e. smoking history, presence of diabetes, cholesterol levels (if known), brief dietary history, usual alcohol intake and exercise levels. History of any previous cardiac or kidney disease, or stroke, or any other significant medical history will be recorded. A list of current medications will be documented.
- Height and weight will be measured.
- A 12-lead electrocardiogram (ECG) will be recorded
- Seated clinic BP measurements will be taken (see below) and heart rate will be recorded.

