# **Statistical Analysis Plan and Data Analysis**

#### Primary Outcome analysis and Sample size estimation

The primary outcome is the association between mean "out of office" systolic BP measured by the HeartGuide watch BP monitor and LVMI measured by cMRI. This relationship will be assessed by Pearson's correlation coefficient for normally distributed data. For the primary outcome, based on 50 cases, using an estimated Pearson's correlation coefficient of 0.30, using data on the relationship between 24-hour ABPM and cMRI LVMI from our prior studies, the power would be 0.56 at P = 0.05. With 50 cases and a correlation coefficient of 0.40, the power would be 0.83 at P = 0.05. For the full analysis with 100 cases (merged analysis with the Jichi Medical University study data), at a correlation coefficient of 0.30, the power is 0.86, and a correlation coefficient of 0.40, the power is 0.99 at P = 0.05.

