#### 23/37

CONFIDENTIAL - HeartGuide BP LVMI Study Protocol - Version 1.0, 09 December 2020 - EDGE 132948; IRAS 280191

- The HeartGuide Watch BP monitor
- b. ABPM
- c. Seated clinic BP
- 4. Relationship between CAVI indices and MRI parameters including;
  - a. LVMI/unindexed LV mass
  - b. Cardiac volumes
  - c. Indices of vascular structure/function
- 5. Relationships and any significant differences between various BP indices measured by:
  - a. The HeartGuide Watch BP monitor
  - b. ABPM
  - c. Seated clinic BP

All data will be analysed for distribution pattern and tested using appropriate methods. Summary statistics for continuous variables will be reported as means and standard deviation or 95% confidence intervals where appropriate. Categorical variables will be reported as n and percentage. Analysis of secondary outcomes will use similar techniques as used for the primary outcome i.e. Pearson's correlation coefficient calculated for the relationships between various BP parameters and cMRI measurements of LV mass, CAVI measurements or ECG voltage criteria for LV mass. The relationship between cMRI parameters and CAVI indices will also be determined using Pearson's correlation coefficient. Additionally, regression coefficients for all relationships will be calculated using linear regression models. Fisher's r to z transformation will be used to compare correlation coefficients between BP modes and MRI or CAVI or ECG-derived parameters. Direct comparison of BP indices will use student's t-tests, one-way ANOVA or other appropriate tests for non-normally distributed data. Data will also be plotted using Bland-Altman plots. Data may also be adjusted for potentially confounding demographic and anthropometric parameters where appropriate. A two-sided significance level of  $P \leq 0.05$  will denote statistical significance. Effect size will also be reported. Due to the relatively small sample size, it is not anticipated that any sensitivity analyses will be carried out.

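### The exclusion criteria protect the BP measurement but not LVMI: people with a known non-pressure cause of raised LV mass can enter the primary correlation of 50

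*Protocol*

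**What the plan says.** - **Why LVMI was chosen.** Background and Purpose of the Study: "hypertrophy of the left ventricle is a validated biomarker of elevated pressure".
- **Who is eligible.** Participants need an office systolic BP of at least 130 mmHg or treated hypertension. Nothing is said about the cause of any hypertrophy. The one cardiac item under Participant Exclusion Criteria is "Current atrial fibrillation or other significant arrhythmia (makes BP measurement unreliable". The wrist and arm limits likewise serve the BP reading, and the remaining items concern consent, pregnancy, feasibility and enrolment in other studies.
- **What happens to cardiac history.** Visit 1: "History of any previous cardiac or kidney disease, or stroke, or any other significant medical history will be recorded". No section uses this record for eligibility or analysis.
- **Primary analysis.** HeartGuide mean systolic BP against cardiac MRI LVMI: "This relationship will be assessed by Pearson's correlation coefficient for normally distributed data". With 50 people, at r = 0.30 "the power would be 0.56 at P = 0.05". Also: "With 50 cases and a correlation coefficient of 0.40, the power would be 0.83 at P = 0.05".
- **Room for correction.** Under Secondary Outcomes, adjustment is optional and limited to demographic and body-size variables, and "it is not anticipated that any sensitivity analyses will be carried out". The same section also says that distributions will be examined and the tests chosen to suit.

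**The concern.** The primary analysis makes sense if LV mass reflects the pressure the heart has worked against. In cardiomyopathy, infiltrative disease or important valve disease, LV mass is set largely by something else. Such a participant adds a large LVMI value that carries little information about the BP measured by the watch. Pearson's r is sensitive to single extreme points, and 50 people is a small sample.

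Two consequences follow. On average the correlation is pulled towards zero, and the power at r = 0.30 is already only 0.56. In any one sample, the direction depends on where the case's BP lies: a well-controlled treated patient with a very heavy ventricle lowers r, and one with high BP raises it. The protocol fixes eligibility, so this part cannot be left to an analysis plan.

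**Working it through.** **1. The protocol's own power.** Inputs are n = 50 or 100, r = 0.30 or 0.40, and two-sided alpha 0.05, all from the Statistical Analysis Plan section. Fisher z approximation: power = Φ(atanh(r)·√(n−3) − 1.96).

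| n | r | atanh(r)·√(n−3) | Power | Protocol |
|---|---|---|---|---|
| 50 | 0.30 | 2.122 | 0.564 | 0.56 |
| 50 | 0.40 | 2.904 | 0.828 | 0.83 |
| 100 | 0.30 | 3.048 | 0.862 | 0.86 |
| 100 | 0.40 | 4.173 | 0.987 | 0.99 |

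The stated figures reproduce, so there is no arithmetic error in the plan.

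**2. Effect if cases are present.** Simulation with 20,000 samples per setting, BP and LVMI bivariate normal in SD units. One or two LVMI values were replaced by N(3, 1) or N(4, 1), independent of BP. Pearson test on everyone; power is the share with positive r and two-sided p ≤ 0.05. Assumptions: the number of cases and the shift. The documents give neither a prevalence nor an LVMI SD.

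| n = 50 | Mean r, true 0.40 | Power | Mean r, true 0.30 | Power |
|---|---|---|---|---|
| No case | 0.395 | 0.831 | 0.297 | 0.570 |
| One, +3 SD | 0.359 | 0.743 | 0.269 | 0.490 |
| One, +4 SD | 0.340 | 0.692 | 0.256 | 0.447 |
| Two, +3 SD | 0.328 | 0.660 | 0.247 | 0.424 |
| Two, +4 SD | 0.299 | 0.576 | 0.224 | 0.355 |

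A repeat with 200,000 samples agreed to within 0.01. In the merged analysis (n = 100, true r = 0.30) power falls from 0.87 simulated to 0.83-0.80 with one case and 0.79-0.73 with two.

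**3. Dependence on the cases' BP.** n = 50, true r = 0.30, two cases at +3 to +4 SD:
- BP 1 SD below the mean: mean r 0.14-0.10, power 0.14-0.06.
- BP 1 SD above the mean: mean r 0.35, power 0.74-0.76.

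**4. Expected loss before knowing whether a case is present.** With prevalence p, the number of cases is Binomial(50, p). Weight the step 2 powers by the chances of none, exactly one, and two or more, counting two or more as two.
- p = 0.5%: weights 0.778, 0.196, 0.026.
- p = 1%: weights 0.605, 0.306, 0.089. Example at r = 0.40, +3 SD: 0.605×0.831 + 0.306×0.743 + 0.089×0.660 = 0.503 + 0.227 + 0.059 = 0.79.
- p = 4%: weights 0.130, 0.270, 0.600.

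| Assumed prevalence | Power, r = 0.40 (+3 to +4 SD) | Power, r = 0.30 (+3 to +4 SD) |
|---|---|---|
| 0.5% | 0.81-0.80 | 0.55-0.54 |
| 1% | 0.79-0.77 | 0.53-0.51 |
| 4% | 0.70-0.64 | 0.46-0.41 |

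**5. Rank correlation.** At true r = 0.30, Spearman power is 0.52 with no case, 0.49 with one and about 0.46-0.45 with two (shifts +3 to +6 SD, BP random). With two cases whose BP is 1 SD below the mean it falls to 0.24-0.22. Ranking limits leverage but leaves the unrelated LVMI values in the sample.

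**The case against.** The case for leaving the plan alone has real force.

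- **Size.** One case moves mean r by about 0.03 to 0.06, against a sampling SD of r of about 0.12-0.13 at n = 50. At a prevalence of 0.5-1% there is a 61-78% chance of no case at all, and step 4 shows an expected loss of a few points of power. This stands.
- **Distribution check.** Pearson is tied to normally distributed data and a suitable alternative is foreseen, so a rank method may be used. This stands in part: in simulation a Shapiro-Wilk test flagged LVMI in only about 22% of samples with one +3 SD case and 52% with one +4 SD case.
- **Broad population.** The watch is meant for diagnosis and monitoring in general, so a wide sample has merit. That is a fair reason to keep any exclusion narrow.

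Two stronger readings are tempting and do not hold. A reader might infer that one or two such cases would erase the primary correlation. With BP unrelated to the condition, two cases at +4 SD still leave mean r at 0.30 from 0.40. Near-zero values (mean r 0.03 at true r = 0.30) need two cases at +6 SD that both have BP 1 SD below the mean. A reader might also infer that a weak result would be blamed on the watch. The protocol correlates ambulatory and office BP with the same LVMI in the same people, so a shared fall would point away from the device.

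**Conclusion.** The point holds in limited form. The eligibility criteria guard one of the two variables in the primary correlation, although the protocol's rationale depends on both. Known non-pressure causes of raised LV mass are admitted, recorded and then ignored. If such cases are present, they weaken the correlation on average and may bias it either way.

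Conditional on one case at +3 to +4 SD with BP unrelated, power drops by about 9 to 14 points at r = 0.40 and 8 to 12 points at r = 0.30. Two cases roughly double that. The expected loss is smaller if prevalence is low. All of this rests on the assumed shift and number of cases, which the documents do not supply. The defect is worth correcting because the remedy is one line. It does not invalidate the design, and the stated power figures are correct for a sample without such cases.

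**What to change.** 1. Add to Participant Exclusion Criteria: *Known non-hypertensive cause of increased LV mass (e.g. cardiomyopathy, infiltrative disease, moderate or severe valve disease)*, applied from the history already taken at Visit 1.
2. Do not add previous myocardial infarction. The Background lists it among the consequences of elevated BP, so excluding it would remove some people with pressure-related damage.
3. Keep participants whose condition is first seen on the study scan in the primary analysis. Removing them would select on the outcome measurement and could trim the upper tail of LVMI. Replace the statement that no sensitivity analysis is expected with one pre-specified supporting analysis that leaves them out. The condition should be identified by a reader who has not seen the BP data; the cardiac MRI section already keeps image readers from linking patient-level data.

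Cost: a few ineligible volunteers, slightly narrower generalisability, one eligibility line and one analysis sentence. No new data collection is needed.
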